## 5.6 Subgroup Analyses for Primary Efficacy Variables

For each treatment cycle, the mean raw value, mean change from study baseline, and 95% CIs for the daily average frequency of normalized daytime urinary incontinence episodes (arithmetic mean) over the 2-day diary period will be presented by treatment group at study visit by

- baseline daytime urinary urgency incontinence episodes (a total of  $\leq 6$  versus  $> 6$ )
- race (Caucasian or non-Caucasian)
- sex (male or female)
- Region (North America versus Other Regions). North America = U.S.A and Canada; Other Regions = Australia, Belgium, Czech Republic, Great Britain, Italy, and Poland.

## 6. Safety Analyses

All analyses will be performed on the BOTOX-treated population. Adverse events and all other safety analyses will be presented by BOTOX treatment cycle in this population and grouped according to the actual dose received at that treatment cycle (25, 50, or 100 U of BOTOX as well as an 'All BOTOX' group).

## **6.1 Study Treatment – Exposure and Administration**

### **6.1.1 Exposure to Study Treatments**

The cumulative duration of treatment exposure will be summarized for the overall study and by each BOTOX treatment cycle. For each patient, the total duration of treatment exposure is defined as the number of days from the day of the first BOTOX treatment to the exit day or the day of data cut, as applicable. For each patient, the number of follow-up days for a given BOTOX treatment cycle is defined as the number of days from the day of treatment to the day prior to the subsequent treatment or exit day or the data cut day, as applicable.

Data will be presented in the following intervals: weeks  $\geq 2$  weeks,  $\geq 6$  weeks,  $\geq 12$  weeks,  $\geq 18$  weeks,  $\geq 24$  weeks,  $\geq 30$  weeks,  $\geq 36$  weeks,  $\geq 42$  weeks,  $\geq 48$  weeks,  $\geq 54$  weeks,  $\geq 60$  weeks,  $\geq 66$  weeks,  $\geq 72$  weeks,  $\geq 78$  weeks,  $\geq 84$  weeks,  $\geq 90$  weeks and  $\geq 96$  weeks. Duration of exposure is based on calendar weeks and descriptive summary statistics of the treatment duration in weeks will be presented.

### **6.1.2 Administration of Study Treatments**

For the BOTOX injection, a patient listing will be produced. The listing will present the time and date of injection and whether the patient was injected per protocol. If the patient was not injected per protocol, the number of injection sites, location of injection sites and volume injected will also be included.

## **6.2 Adverse Events**

AEs will be coded from the verbatim text into preferred term and the primary SOC by using the MedDRA dictionary. Events will be summarized by BOTOX treatment cycle.

A treatment-emergent adverse event (TEAE) for the study treatment period is an AE with onset after the initiation of study treatment or an AE with onset prior to study treatment that worsened in severity or became serious after the initiation of study treatment.

For a given treatment cycle, a TEAE is an AE with onset after the initiation of cycle treatment or an AE with onset prior to cycle treatment that worsened in severity or became serious after the initiation of cycle treatment.

An AE that stops during treatment cycle 1 and recurs in treatment cycle 2 is considered as a TEAE in treatment cycle 2 if it fulfills the TEAE definition above with respect to initiation of cycle 2 treatment.

The incidence of TEAEs will be summarized and presented for all events and will be tabulated by treatment group as follows:

- i. By relationship to treatment. Classified for all TEAEs and treatment-related TEAEs.
- ii. By descending order of frequency.
- iii. By primary SOC and preferred term. At each level of summarization (overall, primary SOC, and preferred term) a patient will be counted once if he/she reports 1 or more experiences at that level.
- iv. By primary SOC, preferred term and severity. For a given adverse event of a patient, if more than 1 severity grade was reported, the worst severity grade will be included in the tabulation. Statistical hypothesis tests will not be performed for this summary.

All treatment-related TEAEs (study drug-related, and injection procedure-related adverse events) will be presented. In addition, study drug-related and injection procedure-related AEs will be presented separately.

Treatment-related TEAEs will be analyzed by the same procedure outlined above (ii, iii, and iv). In addition, the number and percent of patients discontinued due to treatment-related TEAEs will also be tabulated by treatment group.

All the summaries discussed above will be based on all AEs observed during the entire treatment cycle. Since the design of this study allows patients to request/receive retreatment from week 12 (day 84) onward, an additional summary showing the number and percentage of patients with TEAEs by preferred term and treatment group in descending order of incidence will be presented for the TEAE observed prior to or on day 84 after each injection cycle. This will allow for a comparison across dose groups for the same duration of time (ie, since patients can request retreatment from week 12 onwards, patients remain in a cycle for varying time periods). Therefore this analysis provides a more direct comparison across dose groups.

In addition, the number and percentage of patients who have a treatment-emergent UTI during the first 2 weeks (14 days), the first 12 weeks (84 days), and during the overall treatment cycle will be presented by the treatment received in each treatment cycle.

A patient listing will be generated for TEAEs, sorted by primary SOC, preferred term, relationship, and severity. In addition, the number and percent of patients discontinued due to TEAEs will also be tabulated by BOTOX treatment group for each BOTOX treatment cycle. A listing will also be generated for patients who discontinued due to TEAEs.

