100 U BOTOX dose group, whereas in the placebo group it was approximately 28% (Nitti et al, 2013; Chapple et al, 2013). In addition, all secondary endpoints were met in both pivotal studies, which included OAB symptoms and other HRQOL parameters. The duration of effect of BOTOX, based on the first 100 U BOTOX treatment cycle of the pooled phase 3 data integrated with the long-term extension study data, was approximately 6 months.

With respect to safety, adverse events were primarily local adverse events related to the urinary tract, in particular urinary retention and UTI. Treatment with 100 U BOTOX was associated with a transient increase in PVR urine volume, although the majority of patients did not have an increase greater than 100 mL. The limited effect of 100 U BOTOX on PVR was reflected in only 6.5% of patients initiating CIC posttreatment (compared to 0.4% in the placebo group) and the low urinary retention rates.

A consistent efficacy and safety profile has been demonstrated with repeat BOTOX treatment. The reductions from baseline in urinary incontinence episodes remained similar over repeated BOTOX treatments, as did the improvement in HRQOL. The most common adverse events remained urological (eg, UTI and urinary retention), and the incidence of such adverse events did not increase with repeated BOTOX treatment.

Since there was no additional efficacy or benefit with the 150 U BOTOX dose compared with the 100 U BOTOX dose, and given that the 100 U BOTOX dose displayed a better safety profile, 100 U BOTOX was submitted for licensing registration, and approval has subsequently been granted in many countries at this dose.

Use of BOTOX in Pediatric Patients with Overactive Bladder

Following the development of BOTOX for use in adults with urinary incontinence due to OAB, the purpose of Study 191622-137 is to assess the safety and efficacy of BOTOX for the treatment of urinary incontinence in the OAB pediatric population. In this study, patients will receive 25 U, 50 U, or 100 U BOTOX and will have the opportunity to receive multiple treatments over approximately 2 years, with the possibility of dose adjustment based on patient response. The pediatric population to be studied, following discussion with the US Food and Drug Administration (FDA), was defined as patients aged 12 to 17 years.

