## 6.2.1 Potential Distant Spread of Toxin Adverse Events (Applicable to BOTOX Studies Only)

To assess possible distant spread of toxin (PDSOT), 40 MedDRA preferred terms that may be associated with botulinum toxin effects have been identified. All AEs associated with PDSOT will be tabulated by SOC and treatment group; in addition, all PDSOT AEs will be listed by subject. The 40 terms are listed below.

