### 6.3 Serious Adverse Events

A treatment emergent SAE is an TEAE as defined above that further meets one or more SAE criteria at any time during the study treatment period.

The number and percent of patients with serious adverse events will be tabulated by treatment group for all serious adverse events and for treatment-related serious adverse events by SOC for each BOTOX treatment cycle. A listing will be generated of patients with serious adverse events.

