## 6.5 Vital Signs Measurements

Vital signs including pulse rate (beats/min), blood pressure (mm Hg), respiration rate (breaths per minute), and temperature (°C), will be summarized as descriptive statistics for baseline value and change from study baseline by BOTOX treatment group for each BOTOX treatment cycle.

Vital sign values will be considered potentially clinically significant (PCS) if they meet both the observed-value criteria and the change-from-baseline criteria. PCS criteria are specified on Table 5. The number and percentage of patients with PCS postbaseline values will be tabulated for each cycle by treatment group. The percentages will be calculated relative to the number of patients with available non-PCS study baseline values and at least 1 postbaseline assessment in the cycle of interest. The numerator will be the total number of patients with available non-PCS study baseline values and at least 1 PCS postbaseline value in the cycle of interest. A supportive listing of patients with PCS postbaseline values will be provided, including the patient number, baseline and all postbaseline (including non-PCS) values.

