## 6.7 Subgroup Analyses for Safety Variables

The incidences of TEAEs occurring in treatment cycle 1 will be summarized by treatment group for each of the following subgroups: gender (male, female), race (White, Non-White), geographic region (North America vs. Other Regions), and type of anesthesia received (general anesthesia vs. no general anesthesia). The number and percentage of patients reporting TEAE in each treatment group will be tabulated by descending percentage of the preferred terms for each of the subgroups. Since the study design allows patients to request/receive retreatment from week 12 onward, only TEAEs observed prior to or on day 84 after the first study injection will be presented.

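### Several cycle 1 safety tables, including SAEs and treatment-related TEAEs, run over whole cycles of unequal length with no equal-time or exposure-adjusted version

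*SAP*

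**What the plan says.** SAP 6 presents every safety analysis by treatment cycle and by the dose received in that cycle. Within that frame, SAP 6.2 describes the TEAE tables (relationship, frequency, SOC and preferred term, severity), the treatment-related versions, and discontinuations due to treatment-related TEAEs. It then states: "All the summaries discussed above will be based on all AEs observed during the entire treatment cycle".

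Three sets of tables use a fixed window:

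- All TEAEs by preferred term, in every cycle: a summary "will be presented for the TEAE observed prior to or on day 84 after each injection cycle" (SAP 6.2).
- Treatment-emergent UTI: "the first 2 weeks (14 days), the first 12 weeks (84 days), and during the overall treatment cycle will be presented" (SAP 6.2).
- The cycle 1 TEAE subgroups: "only TEAEs observed prior to or on day 84 after the first study injection will be presented" (SAP 6.7).

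The remaining tables have no fixed window:

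- SAEs "will be tabulated by treatment group for all serious adverse events and for treatment-related serious adverse events by SOC for each BOTOX treatment cycle" (SAP 6.3).
- Distant-spread terms: "All AEs associated with PDSOT will be tabulated by SOC and treatment group" (SAP 6.2.1). No window is stated, so the by-cycle rule of SAP 6 applies.
- Discontinuations due to any TEAE: by cycle (SAP 6.2).
- Vital-sign PCS: patients with a non-PCS baseline and "at least 1 PCS postbaseline value in the cycle of interest" (SAP 6.5). Laboratory PCS is defined in the same way (SAP 6.4).

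SAP 6.1.1 defines follow-up days for each cycle, but no safety table uses them as a denominator.

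**The concern.** A cycle ends when the patient is retreated, and SAP 5.5.1 uses time to request or qualification for retreatment as its measure of duration of effect. Cycle length is therefore itself an outcome that the dose may change. Cycle 1 is the only cycle in which dose is randomised; later doses are chosen by the investigator (Protocol 5.5).

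If one dose keeps patients in cycle 1 longer, that group has more time in which events can start. It also has more scheduled visits at which an abnormal vital sign or urinalysis can be recorded. A whole-cycle percentage could then differ between doses even at the same underlying risk. SAP 6.2 accepts this reasoning when it introduces the day-84 table. It gives no reason for stopping short of the serious, treatment-related, distant-spread and discontinuation tables, which matter most for a benefit-risk judgement.

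**Working it through.** The plan states no figure on this point, so there is none to reproduce. The check has three steps.

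**1. How unequal follow-up can be.** Retreatment needs at least 12 weeks since the previous treatment (Protocol 5.10.1). A patient who never requests retreatment exits at week 96 (Protocol Table 1). The range is 96/12 = 8-fold. By the visit list in SAP Table 2, a patient retreated soon after week 12 has 3 scheduled post-treatment clinic visits in cycle 1 (weeks 2, 6 and 12). One never retreated has 10 (those three plus weeks 24, 36, 48, 60, 72, 84 and 96).

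**2. What this does at equal risk.** The 12-week risk p is an assumption, taken as 5%, 10% or 20% and the same in every dose. Let H = −ln(1 − p). A share f of H is an early component complete by week 2, and the rest accrues at a constant rate. Then

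risk by week t = 1 − exp{−[fH + (1 − f)H·t/12]}.

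For p = 10%, H = 0.1054. At t = 24:

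- f = 0: 1 − exp(−0.2107) = 19.0%
- f = 0.5: 1 − exp(−0.1580) = 14.6%
- f = 0.9: 1 − exp(−0.1159) = 10.9%

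| Assumed 12-week risk | Week 24, constant hazard | Week 24, half early | Week 24, 90% early |
|---|---|---|---|
| 5% | 9.8% | 7.4% | 5.5% |
| 10% | 19.0% | 14.6% | 10.9% |
| 20% | 36.0% | 28.4% | 21.8% |

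Cut at day 84, every dose shows the 12-week figure. The 24-week horizon is chosen because the protocol background reports that duration of effect for adult 100 U, from pooled phase 3 and "long-term extension study data, was approximately 6 months". With the planned 32 per group (SAP 1.3), the 10% row is 0.100 × 32 = 3.2 patients at 12 weeks. At 24 weeks it is 0.190 × 32 = 6.1 under a constant hazard, or 0.109 × 32 = 3.5 if 90% is early.

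**3. With a spread of cycle lengths.** Assume retreatment times with a 12-week floor, exponential thereafter, capped at 96 weeks, and a constant 0.3 events per patient-year in every dose. Medians of 24, 16 and 14 weeks give mean cycles of 29.2, 17.8 and 14.9 weeks. Whole-cycle incidence is 15.1%, 9.7% and 8.2%, against 6.7% at 12 weeks for all three. Follow-up differs by 29.2/17.8 = 1.6 to 29.2/14.9 = 2.0. If the medians refer to qualification and 4 weeks are added before injection, the means become about 33.1, 21.8 and 18.9 weeks, and the ratios fall to 1.5 and 1.75. The event rate and the two shorter medians have no source in the documents.

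**The case against.** The strongest reply is that the SAP has already dealt with this. It names the problem and supplies a day-84 table of all TEAEs in every cycle. That table excludes nothing by seriousness, relatedness or distant-spread status, so each such event with onset by day 84 is counted under its preferred term. SAEs, distant-spread events, TEAE discontinuations and PCS values are also listed by patient. This stands, and it narrows the gap to grouped tables. It does not close the gap: preferred-term rows do not show how many patients per dose had any SAE, any treatment-related TEAE or any distant-spread event within the same period.

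A second reply is that constant-hazard figures flatter the concern. Injection-procedure events are likely to cluster early, and treatment-related events need a causal judgement, so background events should add less to them. This also stands, and it is why a range is shown.

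Third, the SAP describes no between-dose safety test, counts are small, and recruitment was stopped early (SAP 15). Whole-cycle capture is also a proper display for SAEs, because a day-84 cut hides late events. All true, and it is a reason to add tables and remove none.

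For blood tests the distortion is weaker. Samples are scheduled before treatment, at week 12 and at exit, so a longer cycle adds no routine blood draw before exit. Vital signs and urinalysis are taken at every clinic visit.

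A reader might infer that only one adverse-event table is cut at equal follow-up. The UTI table and the SAP 6.7 subgroup tables show otherwise.

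**Conclusion.** The gap is real but limited. Outside the all-TEAE, UTI and cycle 1 subgroup summaries, the safety incidence tables named above are per whole cycle, without an equal-time version or an exposure-adjusted rate. If cycle 1 length differs by dose, these tables cannot separate risk from observation time.

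At an assumed 12-week risk of 10% and 24 weeks of follow-up, the excess at equal risk runs from 0.9 percentage points (90% of the hazard early) to 9.0 (constant hazard). It is zero if cycle lengths do not differ.

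A reader might go further and infer that a longer-acting dose will look less safe only because it is watched longer. The documents do not support that. They give no duration by dose in patients aged 12 to 17, and the adult phase 2 study in the protocol background showed a dose-dependent profile for urinary retention and UTI. A true dose effect is therefore plausible, which is a reason to separate it from follow-up time.

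**What to change.** For cycle 1, add day-84 versions of the tables for SAEs, treatment-related TEAEs, TEAEs by severity, grouped distant-spread terms and TEAE discontinuations (SAP 6.2, 6.2.1, 6.3). Do the same for laboratory and vital-sign PCS values (SAP 6.4, 6.5). For these visit-based values, state the cut as through the week 12 analysis visit: its target is Day 85 in SAP Table 2, so a strict Day 84 limit could drop it. The week 12 blood sample covers only complete blood count, BUN and creatinine (Protocol 6.3.14), so the equal-time laboratory table will be limited to those analytes and urinalysis.

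Keep the whole-cycle tables so that late events stay visible. Add to them the number of patients with an event per patient-year, using the follow-up days of SAP 6.1.1 counted to first event or end of cycle. State that between-dose safety statements rest on the equal-time and exposure-adjusted results, read together. The rate alone can mislead in the other direction when events are early: in the 90% early case above, the average weekly hazard is 0.1054/12 = 0.0088 over 12 weeks but 0.1159/24 = 0.0048 over 24 weeks.

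The cost is SAP wording and a few descriptive tables from data already collected. Counts will be small, and events after day 84 will appear only in the whole-cycle and exposure-adjusted tables.

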At each retreatment, the investigator can elect to keep the dose the same or increase the dose one level; if it is deemed that a dose reduction would be warranted then the patient should be exited from the study (see Section 5.5 for further details). The dose decision will be based on the response to the previous treatment. Both the preceding and subsequent dose will remain blinded until the primary analysis has been reported (see Section 7). The dosing options will depend on the investigator's decision as summarized below:

- investigator may elect to keep the same dose as received at the previous treatment (dose not to exceed 6 U/kg)
- investigator may elect to increase the dose compared with the previous treatment (dose not to exceed 6 U/kg) as follows:
 - if the patient received 25 U at the previous treatment, they would receive 50 U
 - if the patient received 50 U at the previous treatment, they would receive 100 U
 - if the patient received 100 U at the previous treatment, they would remain at 100 U

However, for any patient who is already on the highest dose (100 U), if a dose escalation is requested by the investigator on 2 occasions, the patient will be exited from the study upon the second escalation request without receiving any further treatments. In addition, if the investigator assesses that the patient should not be retreated with the current dose and that a dose reduction would be warranted, the patient should be exited from the study as a reduction of dose in this study is not an option. In such cases, the patient will be followed up for a minimum of 12 weeks since their last treatment.

Controls: None

Dosage/Dose Regimen: Multiple treatments may be administered in this study (between 1 and 8 treatments at 25 U, 50 U, or 100 U BOTOX). The first treatment will be administered on day 1 once all “day of treatment criteria” are fulfilled (see Section 5.9.1).

Request for retreatment can occur at scheduled clinic visits, scheduled telephone visits, or between scheduled visits. If the request is made at a scheduled clinic visit, then that visit will also become the qualification for retreatment visit, otherwise a qualification for retreatment clinic visit should be conducted within approximately 1 to 2 weeks of the patient/parent/legally authorized representative request.

The qualification for retreatment criteria are:

- patient/parent/legally authorized representative requests retreatment

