At the qualification for retreatment visit the investigator or designee will contact the IVRS/IWRS and indicate the treatment option for the patient. IVRS/IWRS options will be either to remain at the same dose or to increase the dose since patients will be exited from the study if the investigator assessed that a lower dose was warranted (see below).

In the following 2 scenarios, patients will be exited once a minimum of 12 weeks of follow-up since their last treatment has occurred:

- for any patient who is already on the highest dose (100 U), if a dose escalation is requested by the investigator on 2 occasions, the patient will be exited from the study upon the second escalation request without receiving any further treatments
- for any patient on any dose, if the investigator assesses that they should not be retreated with the current dose but that a dose reduction would be warranted, the patient will be exited from the study as a reduction of dose in this study is not an option

Once all “day of treatment criteria” have been met at the day of treatment visit, the study medication will be allocated via IVRS/IWRS. Study medication will be labeled with medication kit numbers and the IVRS/IWRS will provide the IDR with a specific medication kit number and treatment group assignment for the patient.

Note that retreatments will be blinded until completion of the primary analysis, after which time the investigators will be unblinded to the patients’ initial treatment assignments (see Section 7).

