### 1.1 Primary Study Objectives and Design

The primary objective is to evaluate the safety and efficacy for the treatment of urinary incontinence due to OAB in patients 12 to 17 years of age who have not been adequately managed with anticholinergic therapy.

Patients may participate in the study for 96 weeks following entry into the study and should have at least 12 weeks follow-up since the last treatment prior to exiting the study. Eligible patients are randomized to 1 of 3 treatment groups in a 1:1:1 ratio:

- 25 units (U) BOTOX (not to exceed 6 U/kg)
- 50 U BOTOX (not to exceed 6 U/kg)
- 100 U BOTOX (not to exceed 6 U/kg)

In order to ensure that an upper dosing limit of 6 U/kg is not exceeded, the actual dose administered will be adjusted based on the patient's weight if necessary.

Patients will be centrally randomized. In order to ensure balance across treatment groups, patients will be stratified by baseline daytime urinary urgency incontinence episodes (a total of  $\leq 6$  episodes or  $> 6$  episodes over the 2-day diary collection period).

Multiple treatments may be administered in this study. Doses received at subsequent retreatments will be determined by the investigator and based on the patient's response to the preceding blinded treatment. The investigator can elect to keep the dose the same or increase the dose compared with the preceding treatment. If it is deemed that a decrease in dose is warranted, the patient will be exited from the study. The first treatment will be administered on day 1.

All patients will be evaluated at scheduled clinic visits at weeks 2, 6, and 12 post-treatment, and thereafter at alternating telephone and clinic visits every 6 weeks until the patient qualifies for further retreatment or exits the study. Patients can request retreatment from week 12 since the preceding treatment. Once qualified for retreatment, the same visit schedule will be followed.

The primary efficacy measure is daytime urinary incontinence episodes, and the primary time point is week 12 after treatment 1.

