## 1.3 Sample Size

The sample size calculation for this study is determined empirically. A total of approximately 108 patients are to be enrolled for the study (32 per treatment group plus 10% attrition).

The following table displays the estimated differences between 100 U of BOTOX (maximum 6 U/kg) and 25 U of BOTOX (maximum 6 U/kg) in mean daily average frequency of daytime episodes of urinary incontinence change from baseline at week 12 for a range of common standard deviations (SDs). All calculations assume 32 patients per treatment group and a 2-sided test significance level of 0.05. The calculation was performed using the commercial software nQuery Advisor (procedure MTC0-1), version 6.01 (Statistical Solutions Ltd., Cork, Ireland), and the CI for the difference of 2 means based on normal distribution.

Standard Deviation	Distance From Mean to the Limit
2.0	0.980
2.5	1.225
3.0	1.470
3.5	1.715
4.0	1.960

Note: The ranges of the SDs are determined based on the values from Allergan's 2 pivotal phase 3 OAB studies, 191622-095 and 191622-520. The estimate of the SD for the 100-U BOTOX treatment group is 3.33 for Study 191622-095, 3.58 for Study 191622-520, and 3.46 for the 2 studies combined. The distance from mean to limit indicates how much the CI for the mean extends from the observed difference in means in either direction.

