### 5.2.1 Primary Analyses of Primary Efficacy Variables

The primary efficacy variable is the change from study baseline post treatment 1 in the daily average frequency of daytime urinary incontinence episodes (daytime is defined as the time between waking up to start the day and going to bed to sleep for the night).

Each daytime period recorded in the bladder diary will be normalized to represent a 12-hour period. The daily average frequency of daytime urinary incontinence episodes will be adjusted by the normalized daytime period.

For BOTOX treatment cycle 1, the treatment difference (least-squares [LS] mean difference) and 95% CI of the treatment difference in mean change from study baseline for 100 versus 25 U of BOTOX and 50 versus 25 U of BOTOX will be calculated. Pairwise comparisons of 100 versus 25 U of BOTOX and 50 versus 25 U of BOTOX up to week 12 posttreatment 1 will be evaluated using an ANCOVA model with study baseline value as covariate, and treatment group as factor. A hierarchical analysis strategy ([Lubsen and Kirwan, 2002](#)) to adjust for multiplicity will be used. In the order of (1) 100 versus 25 U of BOTOX, and (2) 50 versus 25 U of BOTOX, treatment group differences at week 12 will be tested at the 0.05 significance level in a fixed sequence fashion. Results of hypothesis testing for 50 versus 25 U of BOTOX will be considered for statistical significance only if the treatment difference for 100 versus 25 U of BOTOX is shown to be statistically significant. A similar analysis, without a hierarchal testing strategy, will be applied to other timepoints.

For each BOTOX treatment cycle, the mean raw value, mean change from study baseline, and 95% CIs for the arithmetic mean change from the study baseline will be summarized by study visit.

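### Dose comparisons after cycle 1 are confounded by earlier response and tolerability, and the SAP 6.2 comparison statement should be limited to cycle 1

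*SAP*

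**What the plan says.** SAP 1.1 describes the initial allocation: "Eligible patients are randomized to 1 of 3 treatment groups in a 1:1:1 ratio". That covers treatment 1 only. For retreatment, the Protocol Summary (Study Treatment Groups) says: "The dose decision will be based on the response to the previous treatment". Protocol 5.5 sets out the selection:

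- The dose goes up one level when the previous dose was tolerated but the response was judged insufficient.
- Where side effects would warrant a lower dose, "the patient will be exited from the study as a reduction of dose in this study is not an option".
- A patient already at 100 U exits on the second escalation request.

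Protocol 5.10.1 also bars retreatment after a treatment-related serious adverse event, and requires a request and at least one daytime urgency incontinence episode in the diary.

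SAP 2.1 assigns the analysis group in each cycle from the dose received in that cycle, and SAP 6 does the same for safety. SAP 5.2.1 specifies the repeated-treatment efficacy output in these terms: "For each BOTOX treatment cycle, the mean raw value, mean change from study baseline", with confidence intervals. Responder rates (SAP 5.3.1) and duration of effect (SAP 5.5.1) are also presented by treatment group within each cycle.

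SAP 6.2 adds a TEAE summary truncated at day 84 and applies it to every injection cycle. The reason given is that patients stay in a cycle for different lengths of time, so truncation equalises the period compared. It concludes: "Therefore this analysis provides a more direct comparison across dose groups".

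**The concern.** Truncating at day 84 deals with unequal exposure time. It does not change who is in each column. In cycle 2 the 25 U column can contain only patients who started at 25 U and were not moved up, so it is enriched for patients who did well. The 100 U column mixes patients randomised to 100 U with patients escalated after an insufficient response at 50 U. Patients who tolerated treatment poorly have partly left. The columns therefore differ in prognosis for both efficacy and adverse events.

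Safety and efficacy of repeated treatment is a stated objective (Protocol 2.1), and by-dose descriptive tables are how it will be reported. For cycle 2 onward the SAP gives no caveat about response-dependent dosing, no adjustment, and no outcome table by initial randomised dose or dose sequence. SAP 3.2 provides only a count of dose switches. A reader could take a flat or reversed efficacy gradient, or a shallow adverse event gradient, as evidence about dose.

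**Working it through.** **The plan's own figures.** SAP 1.3 states: "All calculations assume 32 patients per treatment group and a 2-sided test significance level of 0.05". The half-width is 1.96 × SD × √(2/32) = 0.49 × SD, which gives 0.980, 1.225, 1.470, 1.715 and 1.960 for SDs of 2.0 to 4.0, as tabulated. For attrition, 32/0.9 = 35.6, rounded up to 36 per group, × 3 = 108. Both reproduce, but they describe the randomised cycle 1 comparison. The documents give no precision or bias figure for later cycles, no within-patient correlation and no escalation rate, so those are assumed below.

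**Check 1: responder rate, no dose effect.** Assume 50% responders at every dose, a latent normal response with correlation ρ between cycles, and all patients retreated. Let n be the escalation probability in cycle 1 non-responders and r that in responders.

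- A cycle 1 responder responds again with probability a = 1/2 + arcsin(ρ)/π. A non-responder responds in cycle 2 with probability 1 − a. At ρ = 0.3, a = 0.597; at ρ = 0.7, a = 0.747.
- 25 U column: [(1 − r)a + (1 − n)(1 − a)] / [(1 − r) + (1 − n)].
- 100 U column: [1 + n(1 − a) + ra] / [2 + n + r].
- Mild case (ρ = 0.3, n = 0.6, r = 0.2): 25 U = (0.8 × 0.597 + 0.4 × 0.403)/1.2 = 53%; 100 U = (1 + 0.6 × 0.403 + 0.2 × 0.597)/2.8 = 49%. The gap is about 5 points (4.6 before rounding).
- Strong case (ρ = 0.7, n = 0.9, r = 0.05): 25 U = (0.95 × 0.747 + 0.10 × 0.253)/1.05 = 70%; 100 U = (1 + 0.9 × 0.253 + 0.05 × 0.747)/2.95 = 43%. The gap is 27 points.
- At ρ = 0, a = 0.5, and both columns show 50%.

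The true gap is zero throughout. Tabulated by initial randomised dose, each arm shows 50%.

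**Check 2: responder rate with a true dose effect.** Same model, true rates 50/60/69% at 25/50/100 U, n = 0.8, r = 0.1.

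| Cycle 2 table | 25 U | 50 U | 100 U |
|---|---|---|---|
| By dose received, ρ = 0.3 | 56% | 60% | 67% |
| By dose received, ρ = 0.7 | 66% | 60% | 64% |
| By initial randomised dose, ρ = 0.7 | 55% | 64% | 69% |

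At 0.3 the gradient is attenuated with its order kept. At 0.7 it is lost. The table by initial dose keeps the order but is diluted by escalation: the gap is 69 − 55 = 14 points against a true 69 − 50 = 19.

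**Check 3: change in daily episodes.** This is a simulation of 1.5 million patients per scenario. SAP 1.3 supplies the adult SD: "3.58 for Study 191622-520, and 3.46 for the 2 studies combined". The rest is assumed: total SD 3.46 at all doses, insufficient response meaning a change above −1.0 episodes per day, escalation one level if response was insufficient and no adverse event occurred, half of patients with an adverse event leaving, and everyone else retreated. ICC is the share of response variance that is stable within a patient. Entries are the cycle 2 contrast by dose received, 100 U minus 25 U; negative favours 100 U.

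| True contrast | ICC 0 | ICC 0.3 | ICC 0.5 | ICC 0.7 |
|---|---|---|---|---|
| 0 | 0.0 | +0.8 | +1.3 | +1.8 |
| −1.0 | −1.0 | −0.15 | +0.4 | +0.9 |
| −2.0 | −2.0 | −1.1 | −0.5 | 0.0 |

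The cycle 1 contrast equalled the input in every scenario, apart from simulation error.

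**Check 4: TEAEs, same simulation.** Assumed log-odds of −1.4 at 25 U and a true odds ratio of 2 for 100 U against 25 U. As the SD of patient proneness (logit scale) rises through 0, 0.7, 1.0 and 1.5 alongside the four ICC values, the risk difference goes from cycle 1 to cycle 2 as follows: 13.2 to 13.2, 12.8 to 11.1, 12.2 to 9.5, and 11.0 to 5.9 points. With no true adverse event effect and some heterogeneity, cycle 2 shows a spurious 1 to 4 points in favour of 100 U.

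**The case against.** The SAP sentence is modest. It claims an improvement in directness, for one TEAE summary, relative to the whole-cycle TEAE tables, and gives equal duration as its only reason. A reader might infer that the SAP presents all later-cycle results, including efficacy, as direct dose comparisons. The documents do not support that: no efficacy, responder or duration table is described in those terms.

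The plan also already confines between-dose inference. The pairwise ANCOVA comparisons stop at week 12 after treatment 1 (SAP 5.2.1, 5.4.1), the stratified responder and Treatment Benefit Scale tests are at that timepoint (SAP 5.3.1, 5.4.6), and subgroup safety tables use cycle 1 to day 84 (SAP 6.7). SAP 1.1 and 2.1 state openly that the investigator chooses later doses. Grouping by dose received is a reasonable exposure description for safety.

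The illustrations have limits too. They retreat everyone, or everyone who does not leave for an adverse event, whereas Protocol 5.10.1 excludes patients with no urgency incontinence episode in the diary. If the best 25% are not retreated, the no-effect gap narrows to about 3 to 23 points. Summaries by initial dose are not clean randomised comparisons either, because only retreated patients enter them. SAP section 15 records that recruitment was stopped, so dose-sequence cells may be nearly empty.

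All of this stands and limits the point to interpretation of descriptive tables. It does not justify applying the SAP 6.2 statement to cycles 2 and later, where dose groups are formed by earlier response and tolerability and no caveat is given.

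**Conclusion.** The point holds as a matter of labelling and tabulation. Dose contrasts from cycle 2 onward are confounded. Under the assumed inputs, a responder table with no dose effect shows a false gap of about 5 to 27 points favouring 25 U. A true effect of −1.0 episodes per day is attenuated at ICC 0.3 and reversed at 0.5 and above, while −2.0 is attenuated or erased but not reversed. A true TEAE difference is attenuated, at most from 11.0 to 5.9 points, and not reversed.

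A reader might go further and say that dose effects will be distorted or reversed. That is too strong. The distortion depends on stable differences between patients and vanishes without them, reversal appears only for efficacy and only when the true effect is modest, and the correlations and escalation rates are assumptions. No formal test, sample size or cycle 1 result is affected. What is at stake is how the repeated-treatment tables are read.

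**What to change.** - **SAP 6.2:** limit the statement about comparing dose groups to cycle 1. For later cycles, say only that truncation at day 84 equalises observation time.
- **SAP 5 and 6, cycles 2 and later:** keep the dose-received tables as descriptions of exposure. Footnote them as non-randomised, with dose dependent on earlier response and tolerability, and state that differences between dose columns are not interpreted.
- **Additional summaries:** present later-cycle efficacy and TEAEs by initial randomised dose. Add dose sequence (initial to current dose) only where cell sizes allow; otherwise pool or list.

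The cost is SAP wording and an added grouping variable in existing table programs. It needs no new data and changes no dosing or exit rule. The drawbacks are sparse cells in late cycles, and that tables by initial dose are diluted by escalation and restricted to retreated patients. They should therefore carry a descriptive label as well.
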